11.5. Safety Analyses

All safety endpoints will be evaluated on the Safety population, consisting of all subjects who received at least one dose of study drug and will be analyzed by drug received. Safety will be evaluated by means of AEs (including complications of influenza), clinical laboratory tests, ECGs, vital signs, NEWS, physical examinations, pregnancy testing, and specific toxicities. The safety analysis will be done for the Safety population and for each study phase separately (treatment, follow-up, and the combination of both).

Adverse Events

The verbatim terms used in the eCRF by investigators to identify AEs will be coded using the Medical Dictionary for Regulatory Activities (MedDRA). Treatment-emergent AEs are AEs with onset during the treatment phase or that are a consequence of a pre-existing condition that has worsened since baseline. All reported AEs will be included in the analysis. For each AE, the percentage of subjects who experience at least 1 occurrence of the given event will be summarized by treatment arm. In addition, comparisons between treatment arms will be provided if appropriate.

Summaries, listings, datasets, or subject narratives may be provided, as appropriate, for those subjects who die, who discontinue treatment due to an AE, or who experience a severe or a serious AE.

Clinical Laboratory Tests

Laboratory data will be summarized by type of laboratory test. Reference ranges and markedly abnormal results (specified in the Statistical Analysis Plan) will be used in the summary of laboratory data. Descriptive statistics will be calculated for each laboratory analyte at baseline and for observed values and changes from baseline at each scheduled time point. Changes from baseline results will be presented in pre- vs. post-treatment cross-tabulations (with classes for below, within, and above normal ranges). Frequency tabulations of the abnormalities will be made. A listing of subjects with any laboratory results outside the reference ranges will be provided. A listing of subjects with any markedly abnormal laboratory results will also be provided.

The laboratory abnormalities will be determined according to the criteria specified in the WHO grading table (see [Attachment 1](#)) and in accordance with the normal ranges of the clinical laboratory if no gradings are available. Laboratory abnormalities will be tabulated by scheduled time point.

Electrocardiogram

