3.1.2. Use of Unscheduled Assessments

All scheduled assessments after first administration of trial medication will be used. Unscheduled assessments will not be used in descriptive statistics or any per-time point analysis, but will be shown in listings as applicable. Pre-dose unscheduled assessments will be taken into account for baseline determination and post dose unscheduled assessments will be taken into account for worst-case determination.

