Data will be presented using Kaplan-Meier curves and Kaplan-Meier estimates. For a comparison between treatment arms, the time to hospital discharge in days will be analyzed using an accelerated failure time model. The model will use the parametric shape, selected based on the goodness of fit criterion (AIC), and may take a Weibull, log-logistic, lognormal, or gamma distribution. As baseline covariate the age category (≥ 18 - < 65 years, ≥ 65 - ≤ 85 years) will be included. If the data don't provide an acceptable model fit, alternatively a Cox proportional hazards model can be used (in case the hazards are proportional). In case a Cox proportional hazards model is used a Log-log plot of survival will be added to check the proportional hazard assumption. Additionally, the time to event data will be analyzed using the logrank test and the Gehan-Wilcoxon method.

4.3. **Safety**

All safety analyses will be done on the Safety Set. Analyses will be presented overall and by age category and by treatment group.

4.3.1. *Adverse events*

Pre-treatment AEs are defined as AEs that were reported or worsened after signing the ICF up to the start of study drug dosing. Treatment-emergent AEs (TEAE) are defined as AEs that were reported or worsened on or after the start of study drug dosing through the 28-day Safety Follow-up Visit.

Adverse events with a start date and time recorded will be allocated based on their start date and time. If there is no time recorded for the start of the adverse event the adverse event that occurred on or after the day of first treatment intake and not after the 28-day safety follow up visit will be considered as treatment-emergent. Only adverse events that occur before the day of first medication intake and after/on the day of signing ICF will be considered as pre-treatment.

In case the start date of an adverse event is partially or completely missing, a worst case allocation will be done using the available date and time information in the start and end date time of the adverse event (i.e. if possible based on the available information the adverse event will be allocated to the treatment phase and hospitalization sub period).

Adverse events

The variables related with adverse events are

- AE term (verbatim and MedDRA preferred term and system organ class)
- Onset date, End date and duration of AE
- Serious AE (Yes/No)
- Severity (Mild, Moderate, Severe, Life threatening)

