4.3.2. Clinical laboratory tests

Laboratory parameters of hematology, serum chemistry and urinalysis will be investigated: All analyses will be done on SI-converted values as available in the database.

In case a laboratory test result is *censored* (no numeric value is available, but only a verbatim term), the following rules are applied:

- ‘<x’ or ‘>x’: a numeric value will be imputed by a value exceeding the cut-off value with one unit
- ‘≤x’ or ‘≥x’: imputation by x.

The laboratory abnormalities will be determined according to the criteria specified in the WHO grading table (see Appendix 2), available toxicity grades in the laboratory raw data will not be used. In case no toxicity grades are defined for a test, the abnormalities (above/below normal range) will be used. In determining toxicity grades/abnormalities the following rules are applied:

- Worst grades/abnormalities are determined over the whole observational period for each trial phase separately, including all post-reference scheduled and unscheduled measurements of that phase.
- The abnormalities “abnormally low” and “abnormally high” are considered equally important, i.e. if a subject has as well an abnormally low as an abnormally high value post-reference, both abnormalities are shown in the tables. (This means that the sum of the percentages can be more than 100%)
- If, for a specific test, the grading list provides distinct limits for abnormally low (=hypo) values as well as for abnormally high (=hyper) values, this test should be repeated for hyper and hypo limits separately in cross-tabulations.

Actual values and change from baseline will be summarized by treatment group at each scheduled time point.

An abnormality (toxicity grade or abnormality based on normal ranges) will be considered treatment-emergent in a particular phase if it is worse than the reference corresponding to this phase. If the reference is missing, the abnormality is always considered as treatment-emergent. A shift from “abnormally low” at reference to “abnormally high” post reference (or vice versa) is also treatment-emergent. The treatment emergent definition is applicable in both, the treatment and follow-up phase.

The number and percentage of subjects will be shown in a cross-tabulation of the toxicity/abnormality post-baseline versus baseline at each scheduled time point.

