Additionally, a cross-tabulation of the worst toxicity/abnormality versus baseline will be presented per phase (Treatment phase, Follow-up phase) and for the combination of Treatment and follow-up phase. This table will also show the number and percentage of subjects per worst toxicity/abnormality, the number and percentage of subjects per treatment-emergent worst toxicity/abnormality, and the cumulative number of subjects per treatment-emergent toxicity/abnormality or worse.

Mean \pm SE graphs over time for the actual values and changes from reference will be generated for all tests performed.

A listing of abnormal individual subject hematology and clinical chemistry values from scheduled and unscheduled time points will be provided. This listing will include all other time points for the corresponding subject/parameter.

Grade 2 or higher toxicity laboratory values will be listed separately.

Urinalysis results will be listed. Proteinuria and urine WBCs will be summarized.

4.3.3. *Electrocardiograms*

PR duration, QT duration, QRS duration, Heart Rate and QTc intervals using Bazett’s correction formula and Fridericia’s correction formula will be investigated. QTc values will be used as reported, they will not be recalculated.

The actual values of QT/QTc will be categorized into abnormalities using the boundaries defined in the table below:

Abnormality codes:	QT/QTcorrected
“Normal”	≤ 450 ms
“]450 ms, 480 ms]”	$450 \text{ ms} < \text{QTc} \leq 480$ ms
“]480 ms, 500 ms]”	$480 \text{ ms} < \text{QTc} \leq 500$ ms
“More than 500 ms”	$\text{QTc} > 500$ ms

Abnormalities on the change from reference will be defined for QT/QTc, as follows

- < 30 ms (Normal)
- $[30; 60]$ ms
- > 60 ms.

Only increases by ≥ 30 ms will be considered as abnormalities. (Note: the QTc definitions for abnormalities follow the ICH E14 guidance.)

Worst abnormalities are determined over the whole observational period for each trial phase separately, including all post-reference scheduled and unscheduled measurements of that phase.

An abnormality will be considered treatment-emergent in a particular phase if it is worse than the reference corresponding to this phase. If the reference is missing, the abnormality is always considered as treatment-emergent. Abnormalities on changes from reference are always defined as treatment-emergent.

Actual values and change from baseline will be summarized by treatment group at each scheduled time point.

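### In the SAP 4.3.2 laboratory class tables CPK has only one above-normal class, so marked rises get no by-arm count of their own, and the SAP sets no marked-abnormality limit (minor)

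*SAP*

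**What the plan says.** Protocol 9.3.2 lists CPK in the serum chemistry panel. Neither protocol Attachment 1 nor SAP Appendix 2 has a CPK row; the enzymes graded there in multiples of ULN are AST, ALT, GGT, ALP and amylase. LDH and lipase are in the panel without a row too.

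For such tests SAP 4.3.2 states: "In case no toxicity grades are defined for a test, the abnormalities (above/below normal range) will be used". It also sets aside any grades held in the raw laboratory data. This fallback follows protocol 11.5, which classes results "in accordance with the normal ranges of the clinical laboratory if no gradings are available".

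An abnormality "will be considered treatment-emergent in a particular phase if it is worse than the reference corresponding to this phase". A missing reference, or a shift between abnormally low and abnormally high, also counts. The worst value is taken per phase, "including all post-reference scheduled and unscheduled measurements of that phase".

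Protocol 11.5 says that "markedly abnormal results (specified in the Statistical Analysis Plan) will be used in the summary of laboratory data", and promises a listing of subjects with such results. The SAP does not use the term. Its nearest output is: "Grade 2 or higher toxicity laboratory values will be listed separately".

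**The concern.** With one class above normal, the worst-value, shift and treatment-emergent tables cannot tell a trivial CPK rise from a large one. A subject who is already high at baseline cannot become treatment-emergent high, however far the value climbs. The two outputs that might have separated out marked values do not do so: the Grade 2 or higher listing needs a grade, and the markedly abnormal limit was never set.

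CPK is a reasonable ungraded test to single out. The challenge study described in protocol 1.1 had one severe CPK adverse event on active drug. The drug inhibits OATP1B1 in vitro (protocol 1.1). Protocol 8 disallows other OATP1B1 and OATP1B3 substrates but lets statins continue, with observation for toxicity. At stake is a by-arm laboratory count that separates slight from marked CPK rises, in support of the safety objective.

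**Working it through.** The plan states no figure on this point, so the check applies its rules to example values.

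**Inputs**
- Class for an ungraded test: below, within or above normal (SAP 4.3.2).
- Treatment-emergent high: on-treatment class worse than reference class (SAP 4.3.2). I read worse as a worse class, because the SAP applies the word to a grade or a normal-range abnormality and the tables cross-classify classes.
- Trial ULN classes for comparison: >1 to 2.5, >2.5 to 5, >5 to 10 and >10 x ULN. The upper cut-points are those of the AST/ALT rows in SAP Appendix 2. Those rows start Grade 1 at 1.25 x ULN, whereas the trial classes start just above ULN.
- Optional addition: also count a value of at least 5 x (or 3 x) baseline when baseline is above ULN. Protocol 9.3.6 uses 5 x baseline for AST/ALT discontinuation.
- The CPK values are illustrative and do not come from the documents.

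**Is the rise treatment-emergent?**

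| Baseline to on-treatment, x ULN | Fold | SAP rule | ULN classes | Classes + 5 x baseline | Classes + 3 x baseline |
|---|---|---|---|---|---|
| 0.9 to 1.1 | 1.2 | yes | yes | yes | yes |
| 0.9 to 50 | 56 | yes, same cell as 1.1 | yes, in >10 | yes | yes |
| 1.1 to 2.4 | 2.2 | no | no | no | no |
| 1.5 to 40 | 27 | no | yes | yes | yes |
| 3 to 12 | 4 | no | yes | yes | yes |
| 11 to 50 | 4.5 | no | no | no | yes |
| 11 to 60 | 5.5 | no | no | yes | yes |
| 12 to 13 | 1.1 | no | no | no | no |

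For contrast, ALT going from 1.5 to 12 x ULN moves from Grade 1 to Grade 4 and is treatment-emergent. The same multiples for CPK are above normal to above normal and are not.

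**Largest rise from a high baseline that stays uncounted** (upper class limit divided by lower)
- SAP rule: no limit.
- ULN classes: 2.5/1 = 2.5-fold, 5/2.5 = 2-fold, 10/5 = 2-fold, and no limit above 10 x ULN.
- Adding 5 x or 3 x baseline caps the top class at under 5-fold or under 3-fold.

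**Size.** The documents do not give the share of subjects with CPK above ULN at baseline. As an assumption only, at 5% to 30% of the planned 40 to 60 active subjects it would be 0.05 x 40 = 2 to 0.30 x 60 = 18. That counts subjects with a high baseline, not marked rises missed.

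**What the other outputs carry.** By-visit summaries by arm include the maximum of values and of changes (SAP 3.4 and 4.3.2). They leave out unscheduled draws: "Unscheduled assessments will not be used in descriptive statistics or any per-time point analysis, but will be shown in listings as applicable". Scheduled post-baseline chemistry falls on Days 3, 5, 10 and 28 in hospital, or Days 5, 10 and 28 after discharge (Time and Events Schedules). Among the tabulations, an unscheduled CPK peak therefore enters only the worst-value table, which cannot show its size. The abnormal-value listing does show it.

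**The case against.** The strongest reply is that no information is lost. SAP 4.3.2 lists abnormal chemistry values from scheduled and unscheduled draws, with every other time point for that subject and test, and SAP 3.4 presents listings by treatment group. With at most 90 subjects, a reader can count marked rises by arm from that listing. This stands. A reader might infer that marked CPK rises would vanish from the report, or that an unscheduled peak could not be seen by arm; the documents do not support either.

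Adverse event reporting is a second route. Protocol 9.3.2 has the investigator review each laboratory report and record clinically relevant changes, and SAP 4.3.1 covers worsening: "Treatment-emergent AEs (TEAE) are defined as AEs that were reported or worsened on or after the start of study drug dosing". These events are summarised by severity. This also stands, though it depends on the investigator's judgement.

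Third, the fallback is the protocol's own, so the SAP does not depart from the protocol in using it. High-to-high subjects keep their own shift cell, and a subject at Grade 4 ALT at baseline cannot become worse either. That is correct. Even so, SAP 4.3.3 uses bands together with change categories for QT/QTc, so finer classing fits the plan's own practice.

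Fourth, the case for CPK is modest. It is not a named known risk (protocol 1.4.3), is not among the changes to be closely monitored (1.4.5), and is not a discontinuation limit (9.3.6). The single severe event was 1 of 72 (1.4%) healthy challenge subjects on once-daily regimens, and no placebo CPK figure is given. A reader might infer an established CPK signal; the documents show none. Protocol 8 does not mention CPK or muscle when it refers to statin toxicity, so that link is a clinical judgement.

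Finally, the missing marked-abnormality limit is general and not specific to CPK. The Grade 2 or higher listing is a fair substitute for graded tests, but an ungraded test has none.

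**Conclusion.** The point holds as a minor one, confined to the SAP 4.3.2 class tables and the undefined marked-abnormality limit. For CPK and other ungraded tests, a rise of any size from an above-normal baseline is not laboratory treatment-emergent, and slight and marked rises from a normal baseline fall in one cell. This rests on reading worse as a worse class.

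The only loss is a tabulated by-arm count. How many subjects it would affect cannot be derived. A reader might take the 2 to 18 above as an under-count; it is an assumed number with a high baseline, and few of them may have a marked rise.

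**What to change.** Before unblinding, amend SAP 4.3.2 as follows:

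- Add descriptive CPK classes, for example >1 to 2.5, >2.5 to 5, >5 to 10 and >10 x ULN, and apply the existing worst-value, shift and treatment-emergent rules to them by arm.
- Name >5 x ULN as the markedly abnormal limit for CPK that protocol 11.5 leaves to the SAP. List those values, with a flag for concomitant statin use.
- Optionally, when baseline is above ULN, also count a value of at least a set multiple of baseline. The choice of 3 x or 5 x is a judgement. The 5 x figure is borrowed from a liver-enzyme stopping rule and would leave 11 to 50 x ULN uncounted as treatment-emergent, although that value would appear in the >10 class and in the new listing.

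The cost is a few lines of SAP text and the re-classing of one test, since CPK and concomitant medication are already collected. The cut-points are descriptive: the WHO table has no CPK row, and no document sets a CPK limit. With 40 to 60 active and 20 to 30 control subjects, the upper classes may be empty.

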4.3.5. NEW Score

The NEW Score is an aggregated score with a range from 0 to 20 calculated as the sum of the scores per parameter (see Table 9). In case information for a parameter is missing the NEW score cannot be calculated. Descriptive statistics of the NEW score and the change from baseline will be shown by analysis time point. Additionally a mean \pm SE graph of the scores over time will be provided.

The NEW score will be categorized into its clinical risk according to the following categories:

- Low clinical risk: (score 1 – 4)
- Medium clinical risk: (score 5 – 6, or 1 individual parameter with a score 3)
- High clinical risk: (score 7 and more)

A tabulation of the clinical risk categories will be made per analysis time point.

Table 9: National Early Warning Score (NEWS)*

Physiological Parameters	3	2	1	0	1	2	3
Respiration Rate	≤ 8		9 - 11	12 - 20		21 - 24	≥ 25
Oxygen Saturations	≤ 91	92 - 93	94 - 95	≥ 96			
Any Supplemental Oxygen		Yes		No			
Temperature	≤ 35.0		35.1 - 36.0	36.1 - 38.0	38.1 - 39.0	≥ 39.1	
Systolic BP	≤ 90	91 - 100	101 - 110	111 - 219			≥ 220
Heart Rate	≤ 40		41 - 50	51 - 90	91 - 110	111 - 130	≥ 131
Level Of Consciousness				A			V,P, or U

*The NEWS initiative flowed from the Royal College of Physicians' NEWS Development and Implementation Group (NEWSDIG) report, and was jointly developed and funded in collaboration with the Royal College of Physicians, Royal College of Nursing, National Outreach Forum and NHS Training for Innovation

4.3.6. Physical Examinations:

Abnormal physical examination results will be listed only.

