Blood pressure, pulse/heart rate, respiratory rate, and temperature measurements will be assessed with a completely automated device. Manual techniques will be used only if an automated device is not available.

The level of consciousness will be measured according to the AVPU scale (alert, voice, pain, unresponsive).⁸ Alert: The patient is fully awake (although not necessarily oriented). This patient will have spontaneously open eyes, will respond to voice (although may be confused), and will have bodily motor function. Voice: The patient makes some kind of response when you talk to them, which could be in any of the 3 component measures of eyes, voice, or motor. The response could be as little as a grunt, moan, or slight move of a limb. Pain: The patient makes a response on any of the 3 component measures on the application of pain stimulus, such as a central pain stimulus (sternal rub) or a peripheral stimulus (squeezing the fingers). Unresponsive: Sometimes seen noted as 'Unconscious'; this outcome is recorded if the patient does not give any eye, voice or motor response to voice or pain. The National Early Warning Score (NEWS) will be derived based on vital signs and AVPU scale at baseline and during hospitalization.¹²

Clinically relevant abnormalities (as defined in [Attachment 7](#)) occurring during the study should be recorded in the Adverse Event Section of the eCRF.

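### The NEWS risk classes in SAP 4.3.5 omit score 0 and overlap, and the per-time-point display has no place for discharged or dead patients

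*SAP*

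**What the plan says.** SAP 4.3.5 defines the score as follows: "The NEW Score is an aggregated score with a range from 0 to 20". It then sets three classes: "Low clinical risk: (score 1 – 4", "Medium clinical risk: (score 5 – 6, or 1 individual parameter with a score 3" and "High clinical risk: (score 7 and more". The output is specified in one sentence: "A tabulation of the clinical risk categories will be made per analysis time point". The same section asks for descriptive statistics of the numeric score and a mean ± SE graph over time. It also has a missing-data rule: "In case information for a parameter is missing the NEW score cannot be calculated". It names no denominator, and it has no rule for patients who have gone home or died.

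Protocol 9.3.4 says when the score exists: "The National Early Warning Score (NEWS) will be derived based on vital signs and AVPU scale at baseline and during hospitalization". SAP section 1 says that the SAP is to be read together with the protocol. In the protocol's in-hospital schedule, vital signs are taken three times daily until discharge or Day 14. After discharge they are scheduled on Days 5, 10 and 28, while Days 2 to 4, 6 and 7 are telephone contacts. The footnote that adds level of consciousness to the vital signs appears only on the in-hospital schedule.

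**The concern.** There are two separate problems.

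- **The classes do not partition the scale.** A programmer who follows the text must invent a rule for score 0 and another for patients who meet two definitions. Score 0 is the best possible result, so it matters where it goes.
- **The set of patients behind the display changes over time.** Patients leave it mainly by recovering and being discharged. The arm with more discharges is then represented by its sicker remainder, and both the class percentages and the mean can move against it.

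The protocol (section 11.5) names NEWS among the safety evaluations and asks for its average over time by treatment group. Any interim analysis for regulatory purposes would use the same SAP. A reader who compares the arms on this display could draw the wrong conclusion about direction.

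**Working it through.** **1. Range.** The maximum of each parameter in SAP Table 9, in table order, gives 3 + 3 + 2 + 3 + 3 + 3 + 3 = 20. Every parameter has a 0 column, so the minimum is 0. The stated range is reproduced.

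**2. Classes.** The distinct parameter scores in Table 9 give 4 × 4 × 2 × 4 × 4 × 4 × 2 = 4,096 combinations. The medium rule was read as exactly one parameter at 3.

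- No class: 1 combination, the total of 0. It is the only total left out.
- Low and medium: 31 combinations, with totals of 3 or 4. Six parameters can score 3, which gives 6 combinations with a total of 3. A total of 4 needs one further point from a parameter that can score 1, which gives 5 × 4 + 5 = 25. The sum is 6 + 25 = 31.
- Medium and high: 1,059 combinations, with totals from 7 to 15.

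These are counts of score patterns, not of patients.

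**3. Denominators.** The documents give no NEWS distribution and no discharge rate, so the counts below are assumed. They use the maximum enrolment of 90 at 2:1, that is 60 active and 30 control, at a time point such as Day 7, when discharged patients are only telephoned. Counts are discharged / score 0 / low / medium / high.

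| Assumed counts (active; control) | Medium or high, of all treated | Of those with a score | Of those in a class |
|---|---|---|---|
| Discharge only: 36/0/12/8/4; 10/0/11/6/3 | 12/60 = 20% vs 9/30 = 30% | 12/24 = 50% vs 9/20 = 45% | 50% vs 45% |
| Score 0 only: 0/36/12/8/4; 0/10/11/6/3 | 20% vs 30% | 12/60 = 20% vs 9/30 = 30% | 12/24 = 50% vs 9/20 = 45% |
| Both: 30/12/9/5/4; 8/4/10/5/3 | 9/60 = 15.0% vs 8/30 = 26.7% | 9/30 = 30.0% vs 8/22 = 36.4% | 9/18 = 50.0% vs 8/18 = 44.4% |

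Discharge alone reverses the order when the denominator is patients with a score. The score-0 gap alone reverses it only when the denominator is patients in a class.

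**4. Mean.** Assume average scores of 2.5, 5.5 and 8 within low, medium and high. In the discharge-only row the in-hospital means are (12×2.5 + 8×5.5 + 4×8)/24 = 106/24 = 4.42 for active and (11×2.5 + 6×5.5 + 3×8)/20 = 84.5/20 = 4.23 for control. Counting discharged patients as 0, purely for comparison, gives 106/60 = 1.77 and 84.5/30 = 2.82. Patients who score 0 in hospital stay in the numeric summaries, so the class gap does not move the mean.

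**5. When the order reverses.** Let q be the medium-or-high share of all treated and r the share missing from the denominator through recovery. The table shows q/(1 − r). Active looks worse when q_A/q_C > (1 − r_A)/(1 − r_C). The range tried was r_C of 30% to 50%, with r_A higher by 10 to 30 points.

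- Equal true shares (ratio 1): active always looks worse.
- Active truly 25% lower (ratio 0.75): not at a 10-point difference (at 50% vs 60%, 0.4/0.5 = 0.80), but in every case at 20 points or more (at 30% vs 50%, 0.5/0.7 = 0.71).
- Active truly 50% lower (ratio 0.50): only at 50% vs 80% (0.2/0.5 = 0.40).

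**The case against.** The strongest reply is that the harm depends on a table shell that is not in these documents. SAP 3.4 leaves display details to separate Data Presentation Specifications, and a Safety Set denominator there would prevent the reversal in percentages. SAP 3.4 also requires the number of observations beside each mean, so the shrinking sample would be visible in the descriptive table.

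The in-hospital limit is also less settled than it looks. SAP 4.3.5 does not repeat it, Protocol 11.5 derives the score for each subject from the vital signs, and discharged patients have vital signs scheduled on Days 5, 10 and 28. Protocol 9.3.4 counts level of consciousness among the vital signs.

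Finally, NEWS is in no objective or endpoint list. Recovery is compared through time to improvement of vital signs and respiratory status, the ordinal scale and time to discharge. The ordinal scale is established for all patients on Days 1 to 15 and has categories for death and for patients no longer in hospital. NEWS at baseline enters the vital-signs model as a covariate, and discharge cannot affect a baseline value.

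Most of this stands, and it limits the weight of the point. It does not repair the class definitions, which are wrong as written whatever the shell looks like. Nor does it supply the missing denominator or settle whether an outpatient NEWS exists.

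**Conclusion.** The class definitions are defective on their face: score 0 is unassigned and two pairs of classes overlap. No assumption is needed for that.

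The display problem holds conditionally. If percentages are taken over patients with a score, unequal discharge can make the arm that recovers faster look sicker, and the mean plot is exposed in the same way. The size is unknown. The 50% against 45% in place of 20% against 30% rests on assumed counts, and a large true benefit would be reversed only under extreme differences in discharge. Deaths also leave the display, so the bias need not always favour the same reading.

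A reader might infer more than this, and the documents do not support it:

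- That score-0 patients are certain to drop out of the percentages. No denominator is stated.
- That the score-0 gap raises the mean. Zeros remain in the numeric summaries.
- That discharged patients can never contribute. Outpatient vital signs are scheduled on three days.
- That a trial conclusion is at risk. This is a descriptive safety output with no comparison or decision attached.

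The correction is worth making because it is short, but it does not affect the primary objective or any listed endpoint.

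**What to change.** 1. **Classes.** Define low as a total of 0 to 4 with no parameter at 3. Define medium as a total of 5 or 6, or a total below 5 with any parameter at 3. Define high as a total of 7 or more regardless of single parameters. Every score then falls in exactly one class.
2. **Table.** Use the Safety Set as denominator at each time point, with mutually exclusive rows: low; medium; high; discharged alive with no NEWS; died; in hospital or withdrawn with no calculable score. State the order of assignment.
3. **Mean plot.** Print the number of subjects with a score under each time point and label the plot as in-hospital patients.
4. **Consistency.** Reconcile SAP 4.3.5 with Protocol 9.3.4 on whether the Day 5, 10 and 28 outpatient vital signs give a NEWS. If they do, adjust the label in item 3.

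The cost is a short SAP edit, one revised table shell and a slightly longer table. No new data are needed for the added rows, because hospitalization dates come from the case report form (SAP 3.1.1) and the date of death is collected (Protocol 9.1.5).
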